3.1.1. RESPONSE LOCAL ASSESSMENTS AND ACCORDING TO GMI. ITT

The tables below show the response to treatment at 6 and 12 weeks, based on local assessments of the TACs based on the categorized GMI variable: <1, 1-1.33 and> 3.

Table 82. Response to treatment according to GMI: Local assessment at 6 and 12 weeks ITT

		GMI categorized			p-value	
		<1	1-1.33	> 1.33		Total
		N (% , 95% CI)	N (% , 95% CI)	N (% , 95% CI)		N (% , 95% CI)
Clinical benefit at week 6 (CR, PR or SD) local	No (PD)					
	Yes					
	Total					
Clinical benefit at week 12 (CR, PR or SD) local	No (PD)					
	Yes					
	Total					

1: Chi-square; 2: Fisher's exact test

3.1.2. RESPONSE LOCAL ASSESSMENTS AND ACCORDING TO GMI. PP

Table 83. Response to treatment according to GMI: Local evaluations at 6 and 12 weeks PP

		GMI categorized			p-value	
		<1	1-1.33	> 1.33		Total
		N (% , 95% CI)	N (% , 95% CI)	N (% , 95% CI)		N (% , 95% CI)
Clinical benefit at week 6 (CR, PR or SD) local	No (PE)					
	Yes					
	Total					
Clinical benefit at week 12 (CR, PR or SD) local	No (PE)					
	Yes					
	Total					

1: Chi-square; 2: Fisher's exact test

GEIS-30 STUDY

Statistical analysis plan

3.1.3. RESPONSE LOCAL ASSESSMENTS AND ACCORDING TO GMI. ITT. IN EACH COHORT

The tables shown below show the **response to treatment at 6 and 12 weeks**, in the **ITT population**, based on **local assessments** of TACs based on the categorized GMI variable: <1, 1-1.33 and> 3, separated according to each cohort.

Table 84. Response to treatment according to GMI: local assessments at 6 and 12 weeks ITT. Cohort A

		GMI categorized				p-value
		<1	1-1.33	> 1.33	Total	
		N (% CI)	N (% CI)	N (% CI)	N (% CI)	
Clinical benefit at week 6 (CR, PR or SD) local	No (PD)					
	Yes					
	Total					
Clinical benefit at week 12 (CR, PR or SD) local	No (PD)					
	Yes					
	Total					

1: Chi-square; 2: Fisher's exact test

Table 85. Response to treatment according to GMI: Local assessments at 6 and 12 weeks ITT. Cohort B

		GMI categorized				p-value
		<1	1-1.33	> 1.33	Total	
		N (% CI)	N (% CI)	N (% CI)	N (% CI)	
Clinical benefit at week 6 (CR, PR or SD) local	No (PD)					
	Yes					
	Total					
Clinical benefit at week 12 (CR, PR or SD) local	No (PD)					
	Yes					
	Total					

1: Chi-square; 2: Fisher's exact test

3.1.4. RESPONSE LOCAL ASSESSMENTS AND ACCORDING TO GMI. PP. IN EACH COHORT

The tables shown below show the **response to treatment at 6 and 12 weeks**, in the **PP population**, based on **local assessments** of TACs based on the categorized GMI variable: <1, 1-1.33 and> 3, separated according to each cohort.

Table 86. Response to treatment according to GMI: Local evaluations at 6 and 12 weeks PP. Cohort A

		GMI categorized				p-value
		<1	1-1.33	> 1.33	Total	
		N (% CI)	N (% CI)	N (% CI)	N (% CI)	
Clinical benefit a week 6 (CR, PR or SD) local	No (PD)					
	Yes					

GEIS-30 STUDY

Statistical analysis plan

SD) local	Yes	
	Total	
Clinical benefit at week 12 (CR, PR or SD) local	No (PD)	
	Yes	
	Total	

1: Chi-square; 2: Fisher's exact test

**Table 87. Response to treatment according to GMI: Local assessments at 6 and 12 weeks
PP. Cohort B**

		GMI categorized				p-value
		<1	1-1.33	> 1.33	Total	
		N (% CI)	N (% CI)	N (% CI)	N (% CI)	
Clinical benefit a week 6 (CR, PR or SD) local	No (PD)					
	Yes					
	Total					
Clinical benefit at week 12 (CR, PR or SD) local	No (PD)					
	Yes					
	Total					
1:		Chi-square;	2:	Fisher		exact

GEIS-30 STUDY

Statistical analysis plan

3.2. SECONDARY ENDPOINT PFS ACCORDING TO GMI

3.2.1. PFS ACCORDING TO GMI. LOCAL ASSESSMENT

Figure 7. PFS according to GMI (Local Assessment. ITT). Kaplan-Meier curve.

Table 88. PFS according to GMI (Local assessment. ITT)

	GMI	N (%) events	Median (weeks)	Standard error	95% CI	p-value ¹
PFS	<1					
	1-1.33					
	> 1.33					
	Overall					

1: Log-rank test

Figure 8. PFS according to GMI (Local Assessment. PP). Kaplan-Meier curve.

Table 89. PFS according to GMI (Local assessment. PP)

	GMI	N (%) events	Median (weeks)	Standard error	95% CI	p-value ¹
PFS	<1					
	1-1.33					
	> 1.33					
	Overall					

1: Log-rank test

3.2.2. PFS ACCORDING TO GMI . LOCAL ASSESSMENT. IN COHORT A

Figure 9. PFS according to GMI (local assessment. ITT). Kaplan-Meier curve. Cohort A

Table 90. PFS according to GMI (local assessment. ITT) Cohort A

	GMI	N (%) events	Median (weeks)	Standard error	95% CI	p-value ¹
PFS	<1					
	1-1.33					
	> 1.33					
	Overall					

1: Test of Log- rank

Figure 10. PFS according to GMI (Local assessment. PP). Kaplan-Meier curve. Cohort A

Table 91. PFS according to GMI (local assessment. PP) Cohort A

	GMI	N (%) events	Median (weeks)	Standard error	95% CI	p-value ¹
PFS	<1					
	1-1.33					
	> 1.33					
	Overall					

GEIS-30 STUDY

Statistical analysis plan

1: Log Test- rank

3.2.3. PFS ACCORDING TO GMI. LOCAL ASSESSMENT. IN COHORT B

Figure 11. PFS according to GMI (local assessment. ITT). Kaplan-Meier curve. Cohort B

Table 92. PFS according to GMI (local assessment. ITT) Cohort B

	GMI	N (%) events	Median (weeks)	Standard error	95% CI	p-value ¹
	<1					
PFS	1-1.33					
	Overall					

1: Log-rank test

Figure 12. PFS according to GMI (Local assessment. PP). Kaplan-Meier curve. Cohort B

Table 93. PFS according to GMI (local assessment. PP) Cohort B

	GMI	N (%) events	Median (weeks)	Standard error	95% CI	p-value ¹
	<1					
PFS	1-1.33					
	Overall					

1: Log-rank test

3.3. SECONDARY ENDPOINT OS ACCORDING TO GMI

3.3.1. OS ACCORDING TO GM.

Figure 13. OS according to GMI (ITT). Kaplan-Meier curve.

Table 94. OS according to GMI (ITT)

	GMI	N (%) events	Median (weeks)	Standard error	95% CI	p-value ¹
	<1					
	1-1.33					
	> 1.33					
OS	Overall					

1: Log-rank test

GEIS-30 STUDY

Statistical analysis plan

Figure 14. OS according to GMI (PP). Kaplan-Meier curve.

Table 95. OS according to GMI (PP)

	GMI	N (%) events	Median (weeks)	Standard error	95% CI	p-value ¹
OS	<1					
	1-1.33					
	> 1.33					
	Overall					

1: Log-rank test

3.3.2. OS ACCORDING TO GMI. IN COHORT A

Figure 15. OS according to GMI (ITT). Kaplan-Meier curve. Cohort A

Table 96. OS according to GMI (ITT) Cohort A

	GMI	N (%) events	Median (weeks)	Standard error	95% CI	p-value ¹
OS	<1					
	1-1.33					
	> 1.33					
	Overall					

1: Log-rank test

Figure 16 OS according to GMI (PP). Kaplan-Meier curve. Cohort A

Table 97. OS according to GMI (PP) Cohort A

	GMI	N (%) events	Median (weeks)	Standard error	95% CI	p-value ¹
OS	<1					
	1-1.33					
	> 1.33					
	Overall					

1: Log-rank test

3.3.3. OS ACCORDING GMI. IN COHORT B

Figure 17. OS according to GMI (ITT). Kaplan-Meier curve. Cohort B

Table 98. OS according to GMI (ITT) Cohort B

	GMI	N (%) events	Median (weeks)	Standard error	95% CI	p-value ¹
OS	<1					
	> 1.33					
	Overall					

1: Log-rank test

GEIS-30 STUDY

Statistical analysis plan

Figure 18. OS according GMI (PP). Kaplan-Meier curve. Cohort B

Table 99. OS according to GMI (PP) Cohort B

	GMI	N (%) events	Median (weeks)	Standard error	95% CI	p-value ¹
	<1					
OS	> 1.33					
	Overall					

1: Log-rank

GEIS-30 STUDY

Statistical analysis plan

3.4. ECOG test (BASAL) ACCORDING GMI

3.4.1. ECOG BASAL ACCORDING TO GMI. ITT

The following tables analyze the possible relationship between the variables ECOG baseline and categorized GMI: <1, 1-1.33 and > 3.

Table 100. Baseline ECOG according to GMI (ITT)

	GMI categorized				p-value
	<1	1-1.33	> 1.33	Total	
	N (% , 95% CI)	N (% , 95% CI)	N (% , 95% CI)	N (% , 95% CI)	
Performance status	0				
	1				
	Total				

1: Chi-square; 2: Fisher exact test

3.4.2. ECOG BASAL ACCORDING TO GMI. PP

Table 101. Baseline ECOG according to GMI (PP)

	Categorized GMI				p-value
	<1	1-1.33	> 1.33	Total	
	N (% , 95% CI)	N (% , 95% CI)	N (% , 95% CI)	N (% , 95% CI)	
Performance status	0				
	1				
	Total				

1: Chi-square; 2: Fisher's exact test

3.5. GRADE FNCLCC (BASAL) ACCORDING TO GMI

3.5.1. GRADE FNCLCC BASAL ACCORDING TO GMI. ITT

The following tables analyze the possible relationship between the variables grade FNCLCC baseline and categorized GMI: <1, 1-1.33 and > 3.

Table 102. GRADE FNCLCC baseline according to GMI (ITT)

	GMI categorized				p-value
	<1	1-1.33	> 1.33	Total	
	N (% , 95% CI)	N (% , 95% CI)	N (% , 95% CI)	N (% , 95% CI)	
GRADE FNCLCC	1				
	2				
	3				
	Total				0.017 ²

1: Chi-square; 2: Fisher's exact test

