## **5. STUDY DESIGN**

### **5.1. Development Phase**

A two cohort Phase II, open-label, non-randomized, multi-center study with 5 centres in Spain and 5 centres in Germany to evaluate the activity and tolerability of Pazopanib in patients with advanced and/or metastatic liposarcoma who have relapsed following standard therapies or for whom no standard therapy exists.

The drug will be separately investigated in the following liposarcoma subtypes (cohorts):

- Well-differentiated liposarcoma/de-differentiated liposarcoma (ALT-WD)
- Myxoid/round cell liposarcoma.

A total of 17 eligible and treated patients will be included (in each stratum) in the first step of the study. If  $\leq 3$  successes are observed in a stratum, the trial will be stopped in this stratum with the conclusion that the drug should not be further investigated in this histology. Otherwise, patients will continue to be accrued. Each cohort will independently recruit a maximum of 37 patients. The statistical analysis will be performed in each stratum.

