### **10.4. Sample Size and Statistical analysis**

The drug will be separately investigated in the following liposarcoma subtypes:

- Well-differentiated liposarcoma/dedifferentiated liposarcoma (ALT-WD)
- Myxoid/round cell liposarcoma.

The Simon two-stage design will be separately applied in each stratum. A total of 17 patients will be included in each stratum for the first step of the trial. For the second step, 20 (up to 37) additional patients will enter in each stratum provided the results of the first step were positive. A total of 37 patients could enter the study in each stratum.

Success will be defined as documented disease stabilization or response after at least 12 weeks of therapy.

The following design characteristics and decision rules apply separately to each stratum. The Simon optimal one sample two stages testing procedure (optimal design) will be used with the following hypotheses:

- Success in 20% of the cases or less in one of the strata will be considered as unacceptable, and would not warrant further investigation (null hypothesis). Therefore, the value of P0 will be taken as 20%.
- Success in 40% of the cases or more in one of the strata will be considered as an acceptable result warranting further investigation of the drug in this histology (alternative hypothesis). Therefore, the value of P1 will be taken as 40%.

These two reference values are based on a retrospective analysis of the EORTC STBSG database of patients treated with 2nd line therapy.

Under those hypotheses, a total of 37 eligible and treated patients will need to be recruited in each stratum and followed for at least 12 weeks. The size of the type I and type II errors is 10% ( $\alpha=\beta=0.1$ ).

A total of 17 eligible and treated patients will be included (in each stratum) in the first step of the study.

1. If  $\leq 3$  successes are observed in a stratum, the trial will be stopped in this stratum with the conclusion that the drug should not be further investigated in this histology.
2. Else, patients will continue to be accrued until 37 eligible patients have been recruited and have started therapy. If 11 or more successes are observed in those 37 patients, we will conclude that the results of this trial warrant further investigation in this histology.

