1.10. DESIGN

Phase II study of two cohorts, open, non-randomized and multicenter with 11 participating centers in Spain and 5 in Germany. To evaluate the activity and tolerability of pazopanib in patients with advanced and / or metastatic liposarcoma who have relapsed after standard treatment or for whom there is no established treatment.

The drug will be investigated separately in the following liposarcoma subtypes (cohorts):

- Well-differentiated liposarcoma / dedifferentiated liposarcoma (ALT-WD)
- Myxoid liposarcoma / round cell liposarcoma.

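### Baseline ECOG and FNCLCC grade are crossed with GMI only in the pooled cohorts, so the test can pick up a histology difference if the cohorts differ in both variables

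*SAP*

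**What the plan says.** Protocol 5.1 sets up two liposarcoma cohorts, well-differentiated/dedifferentiated and myxoid/round cell, and adds: "The statistical analysis will be performed in each stratum". SAP 1.10 repeats the principle: "The drug will be investigated separately in the following liposarcoma subtypes (cohorts".

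Annex I of the SAP relates GMI, in three classes (<1, 1-1.33, >1.33), to other variables:

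- Response, PFS and OS by GMI (3.1 to 3.3) appear pooled and then again for cohort A and cohort B.
- Section 3.4.1 looks at the "possible relationship between the variables ECOG baseline and categorized GMI". Tables 100 (ITT) and 101 (PP) have the GMI classes and a total as columns, with one p-value and no cohort split.
- Section 3.5.1 looks in the same way at the "possible relationship between the variables grade FNCLCC baseline and categorized GMI", in Table 102 (ITT). The test is chi-square or Fisher's exact.
- The SAP index lists only ITT and PP versions of 3.4 and 3.5. The body of 3.5.2 is not in the text available here, so its pooled layout is read from the index.

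Table 102 has empty cells but carries a p-value of 0.017, footnoted as Fisher's exact test. The SAP states no significance level for this annex.

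**The concern.** Tables 100 to 102 ask whether grade or performance status goes with better growth modulation on pazopanib. Pooling two histologies adds a second route to a positive answer. If one cohort has both more high-grade patients and more patients with a high GMI, the pooled table shows grade and GMI moving together even when they are unrelated inside each cohort. A reader would then take a difference between histologies for an effect of grade or ECOG.

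These are the GMI analyses in the annex that have no cohort version to set beside the pooled one. The margins are reported by cohort elsewhere (grade in Table 20, ECOG in Table 73, GMI in Tables 69 to 72), but the margins do not show whether an association holds within a cohort. Table 102 also already holds a nominally significant p-value that could be reported as a grade effect.

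**Working it through.** **1. The plan's own design figure.** Protocol 10.4 gives P0 = 0.20, P1 = 0.40, 17 then 37 patients per stratum, stop at 3 or fewer successes, positive at 11 or more. The probability of a positive result is the sum over x = 4 to 17 of P(X1 = x; 17, p) × P(X2 ≥ 11 − x; 20, p). This gives 0.0948 at p = 0.20 and 0.9033 at p = 0.40. The stopping probability under P0 is 0.549, so the expected N is 17 + 20 × (1 − 0.549) = 26.0. The design reproduces and is per stratum: "The following design characteristics and decision rules apply separately to each stratum". Nothing below touches it.

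**2. When pooling creates an association.** Let cohort A be a share w of the patients. Let g be the share in a given grade (or ECOG) class and m the share in a given GMI class, independent within each cohort. Then

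pooled cell share − product of pooled margins = w(1 − w)(gA − gB)(mA − mB).

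This is zero if either difference is zero, so a cohort difference in grade alone, or in GMI alone, creates no association. For Grade 3 with GMI >1.33, equal cohorts and 74 patients:

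- mild: 0.25 × (0.40 − 0.25) × (0.35 − 0.20) = 0.0056, or 0.4 patients
- moderate: 0.25 × (0.50 − 0.20) × (0.40 − 0.15) = 0.0188, or 1.4 patients
- strong: 0.25 × (0.65 − 0.10) × (0.50 − 0.10) = 0.055, or 4.1 patients

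**3. Assumed distributions.** The documents give none. GMI is listed as <1 / 1-1.33 / >1.33, cohort A v cohort B.

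- Mild: grade 1/2/3 15/45/40% v 30/45/25%; ECOG 0/1 40/60% v 55/45%; GMI 50/15/35% v 65/15/20%.
- Moderate: grade 10/40/50% v 40/40/20%; ECOG 30/70% v 60/40%; GMI 40/20/40% v 70/15/15%.
- Strong: grade 5/30/65% v 55/35/10%; ECOG 20/80% v 75/25%; GMI 35/15/50% v 80/10/10%.
- Grade only: grade 20/30/50% v 20/60/20%; the same GMI in both cohorts.

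**4. Rejection rates.** There is no association inside either cohort, and 0.05 is an assumed level (the only 5% level in the documents is for the translational study). The pooled test is Fisher's exact. The stratified test is generalised Cochran-Mantel-Haenszel (CMH) by cohort. Runs per scenario: grade 4,000 (37 per cohort) and 6,000 (20 per cohort); ECOG 3,000. Each cell shows 37 / 20 per cohort.

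| Cohort difference | Grade, pooled | Grade, stratified | ECOG, pooled | ECOG, stratified |
|---|---|---|---|---|
| None | 5.2% / 4.7% | 4.8% / 4.0% | 5.0% / 4.7% | 5.0% / 4.6% |
| Grade only | 4.3% / 5.3% | 3.6% / 4.2% | – | – |
| Mild in both | 5.0% / 4.9% | 4.3% / 3.8% | 4.8% / 4.6% | 4.5% / 4.0% |
| Moderate in both | 11.6% / 7.6% | 4.9% / 4.3% | 9.5% / 6.9% | 4.6% / 4.1% |
| Strong in both | 57.6% / 32.8% | 3.6% / 3.3% | 50.3% / 29.8% | 3.9% / 4.3% |

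The simulation error near 5% is at most √(0.05 × 0.95 / 3000) = 0.4 percentage points.

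**5. Sample size.** GMI needs a time to progression on a previous line. Inclusion criterion 8 admits patients judged ineligible for chemotherapy, who may have had no such line. So 37 per cohort is an upper bound, and the 20-per-cohort figures show a smaller case.

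**6. The printed 0.017.** It cannot be recomputed or split by cohort, because the cells of Table 102 are blank.

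**The case against.** The strongest reply is that inflation is conditional and its conditions are unproven. That stands: both variables must differ between cohorts, and by more than a mild amount. The fact that the SAP tests grade and GMI between cohorts shows little, since most of its baseline tables carry such a p-value, including weight and sodium. Eligibility is limited to high or intermediate grade, which narrows the room for a grade difference and makes the strong grade scenario, with 55% Grade 1 in one cohort, hard to expect. If only two grades occur, the ECOG columns apply for the same shares. No document gives a reason for ECOG to differ by histology.

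A reader might infer from "Table 92. PFS according to GMI (local assessment. ITT) Cohort B", and from Table 93, that cohort B has no patient with GMI >1.33, and so that GMI does differ. The documents do not support this. Tables 98 and 99, for the same cohort, include >1.33 and omit 1-1.33, and Tables 85 and 87 show all three classes. The shells contradict each other and are not evidence of an empty class.

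It can also be argued that the per-stratum sentence in protocol 5.1 follows the stopping rule and governs the two-stage design only, and that the SAP has pooled GMI tests elsewhere. The sentence carries no exception, however, and those other pooled tests are accompanied by cohort versions. The gap is best read as an omission, not as a clear breach.

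Finally, separate cohort tables will be sparse. That is a reason to combine the cohorts through a stratified test, not to ignore cohort.

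**Conclusion.** The point holds in a conditional form. Sections 3.4 and 3.5 plan pooled tables only, and their test does not separate histology from grade or ECOG. With no relation inside either cohort, the pooled test's error is about 5% if the cohorts differ in one variable only or mildly in both. It is about 7-12% for moderate differences in both and about 30-58% for strong ones, at 20 to 37 patients per cohort. The stratified test stays at 3.3-5.0% throughout. The cohort distributions and the 5% level are assumptions, and the documents do not show where this trial falls.

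Two stronger conclusions do not follow. The 0.017 in Table 102 is not shown to be a histology artefact; it may or may not be. Nor does a histology difference in grade alone produce a false association. The analysis is exploratory, no decision hangs on it, and the correction is minor.

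**What to change.** In SAP 3.4 and 3.5:

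- Show the ECOG-by-GMI and grade-by-GMI tables for cohort A and cohort B, in ITT and PP, as Annex I already does for response, PFS and OS.
- Base the p-value on one cohort-stratified test: an exact or generalised CMH test, or a permutation test within cohort.
- Keep a pooled table if wanted, but label any pooled p-value, including the printed 0.017, as descriptive.

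The cost is a few more tables and a standard test on data already collected. The cohort tables will be sparse, most of all in a cohort stopped after about 17 patients, fewer of them with a GMI. There is a small loss of power if the cohorts do not differ.
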